### Trademark Information

Trademarks of the GlaxoSmithKline group of companies
NONE

Trademarks not owned by the GlaxoSmithKline group of companies
CredibleMeds
FACTS
SAS
WinNonlin

## 14.2. Appendix 2: ECOG Performance Status

The performance status assessment is based on the ECOG scale [[Oken, 1982](#)]

0 = Fully active, able to carry on all pre-disease performance without restriction.

1 = Restricted in physically strenuous activity but ambulatory and able to carry out work of a light or sedentary nature (e.g., light house work, office work).

2 = Ambulatory and capable of all self-care but unable to carry out any work activities. Up and about more than 50% of waking hours.

3 = Capable of only limited self-care, confined to bed or chair more than 50% of waking hours.

4 = Completely disabled. Cannot carry on any self-care. Totally confined to bed or chair.

5 = Dead.

### 14.3. Appendix 3: Liver Safety Required Actions and Follow up Assessments

**Phase I/II liver chemistry stopping and increased monitoring criteria** have been designed to assure subject safety and to evaluate liver event etiology (in alignment with the FDA premarketing clinical liver safety guidance).

<http://www.fda.gov/downloads/Drugs/GuidanceComplianceRegulatoryInformation/Guidances/UCM174090.pdf>.

#### Phase I/II liver chemistry stopping criteria and required follow up assessments

Liver Chemistry Stopping Criteria – Liver Stopping Event Subject with entry criteria ALT ≤ 2.5 x ULN	
ALT-absolute	ALT ≥ 5xULN
ALT Increase	ALT ≥ 3xULN persists for ≥4 weeks
Bilirubin	ALT ≥ 3xULN and bilirubin ≥ 2xULN (>35% direct bilirubin)
INR^2	ALT ≥ 3xULN and INR>1.5, if INR measured
Cannot Monitor	ALT ≥ 3xULN and cannot be monitored weekly for 4 weeks
Symptomatic	ALT ≥ 3xULN associated with symptoms (new or worsening) believed to be related to liver injury or hypersensitivity
Liver Chemistry Stopping Criteria – Liver Stopping Event Including subjects with documented liver metastases/tumor infiltration at baseline AND entry criteria ALT>2.5 x ULN but ≤5 x ULN	
ALT-absolute	Both ALT ≥ 5xULN and ≥2x baseline value
ALT Increase	Both ALT ≥ 3xULN and ≥ 1.5x baseline value that persists for ≥4 weeks
Bilirubin	ALT ≥ 3xULN and bilirubin ≥ 2xULN (>35% direct bilirubin)
INR^2	ALT ≥ 3xULN and INR>1.5, if INR measured
Cannot Monitor	Both ALT ≥ 3xULN and ≥ 1.5x baseline value that cannot be monitored for 4 weeks
Symptomatic	Both ALT ≥ 3xULN and ≥ 1.5x baseline value associated with symptoms (new or worsening) believed to be related to liver injury or hypersensitivity

Required Actions and Follow up Assessments following ANY Liver Stopping Event	
Actions	Follow Up Assessments

 
• Immediately discontinue study treatment
 
• Report the event to GSK within 24 hours
 
• Complete the liver event CRF and complete an SAE data collection tool if the event also meets the criteria for an SAE
 
• Perform liver event follow up assessments
 
• Monitor the subject until liver chemistries resolve, stabilize, or return to within baseline (see MONITORING below)
 
• Do not restart/rechallenge subject with study treatment unless allowed per protocol and GSK Medical Governance approval is granted (refer to Appendix 4)
 
• If restart/rechallenge not allowed per protocol or not granted, permanently discontinue study treatment and may continue subject in the study for any protocol specified follow up assessments
 
 
MONITORING:
 
For bilirubin or INR criteria:
 
 
• Repeat liver chemistries (include ALT, aspartate aminotransferase [AST], alkaline phosphatase, bilirubin) and perform liver event follow up assessments within 24 hrs
 
• Monitor subjects twice weekly until liver chemistries resolve, stabilize or return to within baseline
 
• A specialist or hepatology consultation is recommended
 
 
For All other criteria:
 
 
• Repeat liver chemistries (include ALT, AST, alkaline phosphatase, bilirubin) and perform liver event follow up assessments within 24-72 hrs
 
• Monitor subjects weekly until liver chemistries resolve, stabilize or return to within baseline
 
	
 
• Viral hepatitis serology
 
• Only in those with underlying chronic hepatitis B at study entry (identified by positive hepatitis B surface antigen) quantitative hepatitis B DNA and hepatitis delta antibody
 
• Blood sample for pharmacokinetic (PK) analysis, obtained 2 days after last dose
 
• Serum creatine phosphokinase (CPK) and lactate dehydrogenase (LDH).
 
• Fractionate bilirubin, if total bilirubin <math>\geq 2 \times \text{ULN}</math>
 
• Obtain complete blood count with differential to assess eosinophilia
 
• Record the appearance or worsening of clinical symptoms of liver injury, or hypersensitivity, on the AE report form
 
• Record use of concomitant medications on the concomitant medications report form including acetaminophen, herbal remedies, other over the counter medications
 
• Record alcohol use on the liver event alcohol intake case report form
 
 
For bilirubin or INR criteria:
 
 
• Anti-nuclear antibody, anti-smooth muscle antibody, Type 1 anti-liver kidney microsomal antibodies, and quantitative total immunoglobulin G (IgG or gamma globulins).
 
• Serum acetaminophen adduct HPLC assay (quantifies potential acetaminophen contribution to liver injury in subjects with definite or likely acetaminophen use in the preceding week [James, 2009]).
 
• Liver imaging (ultrasound, magnetic resonance, or computerised tomography) and /or liver biopsy to evaluate liver disease; complete Liver Imaging and/or Liver Biopsy CRF forms.
 


1. Serum bilirubin fractionation should be performed if testing is available. If serum bilirubin fractionation is not immediately available, discontinue study treatment for that subject if ALT  $\geq$  3xULN **and** bilirubin  $\geq$  2xULN. Additionally, if serum bilirubin fractionation testing is unavailable, **record presence of detectable urinary bilirubin on dipstick**, indicating direct bilirubin elevations and suggesting liver injury.
2. All events of ALT  $\geq$  3xULN **and** bilirubin  $\geq$  2xULN (>35% direct bilirubin) or ALT  $\geq$  3xULN **and** INR>1.5, if INR measured which may indicate severe liver injury (possible 'Hy's Law'), **must be reported as an SAE (excluding studies of hepatic impairment or cirrhosis)**; INR measurement is not required and the threshold value stated will not apply to subjects receiving anticoagulants
3. New or worsening symptoms believed to be related to liver injury (such as fatigue, nausea, vomiting, right upper quadrant pain or tenderness, or jaundice) or believed to be related to hypersensitivity (such as fever, rash or eosinophilia)
4. Includes: Hepatitis A IgM antibody; Hepatitis B surface antigen and Hepatitis B Core Antibody (IgM); Hepatitis C RNA; Cytomegalovirus IgM antibody; Epstein-Barr viral capsid antigen IgM antibody (or if unavailable, obtain heterophile antibody or monospot testing); Hepatitis E IgM antibody
5. If hepatitis delta antibody assay cannot be performed, it can be replaced with a PCR of hepatitis D RNA virus (where needed) [Le Gal, 2005].
6. Record the date/time of the PK blood sample draw and the date/time of the last dose of study treatment prior to blood sample draw on the CRF. If the date or time of the last dose is unclear, provide the subject's best approximation. If the date/time of the last dose cannot be approximated OR a PK sample cannot be collected in the time period indicated above, do not obtain a PK sample. Instructions for sample handling and shipping are in the Laboratory Manual.

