**Table 4 Definitions for Adequate Organ Function**

System	Laboratory Values
Hematologic	
Absolute neutrophil count (ANC)	$\geq 1.5 \times 10^9/L$
Hemoglobin	$\geq 9$ g/dL (subjects that required transfusion or growth factor need to demonstrate stable hemoglobin for 7 days of 9 g/dL)
Platelets	$\geq 100 \times 10^9/L$
PT/INR and PTT	$\leq 1.5 \times$ upper limit of normal (ULN)
Hepatic	
Albumin	$\geq 2.5$ g/dL
Total bilirubin	$\leq 1.5 \times$ ULN (isolated bilirubin $>1.5 \times$ ULN is acceptable if bilirubin is fractionated and direct bilirubin $<35\%$ or subject has a diagnosis of Gilbert's syndrome)
Alanine aminotransferase (ALT)	$\leq 2.5 \times$ ULN OR $<5 \times$ ULN is acceptable for subjects with documented liver metastases/tumor infiltration
Renal	
Creatinine	$\leq 1.5 \times$ ULN
OR	
Creatinine clearance [either directly measured or calculated by Cockcroft-Gault formula b ]	$\geq 40$ mL/min
Cardiac	
Ejection fraction	$\geq 50\%$ by echocardiogram
Troponin (T)	$\leq$ ULN
Potassium	$\geq$ Lower limit of normal (LLN) and $\leq$ ULN
Magnesium	$\geq$ LLN a

- a. Magnesium supplementation is permitted, as required, to maintain a serum magnesium concentrations  $\geq$  LNN
  - b. Cockcroft and Gault Method for Calculated Creatinine Clearance is provided in [Appendix 9](#).
- 
8. Able to swallow and retain orally administered medication.
  9. A female subject is eligible to participate if she is of:

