## 5.2. Exclusion Criteria

A subject will not be eligible for inclusion in this study if any of the following criteria apply:

1. Primary malignancy of the central nervous system or malignancies related to human immunodeficiency virus (HIV) or solid organ transplant.
2. Recent prior therapy, defined as follows:

- a. Any investigational or Food and Drug Administration (FDA)-approved anti-cancer drug within 14 days or 5 half-lives, whichever is longer, prior to the first dose of GSK2820151. Note that an investigational drug is defined as a drug without an approved oncologic indication
  - b. Any radiotherapy, chemotherapy, targeted therapy or immunotherapy within 14 days or major surgery within 28 days or anti-neoplastic antibody or nitrosoureas/mitomycin C within 42 days prior to the first dose of GSK2820151.
  - c. Anti-androgen (e.g., bicalutamide) therapies for prostate cancer,, must be stopped 4 weeks prior to the first dose of GSK2820151. Second-line hormone therapies such as enzalutamide, abiraterone, or orteronel should be stopped 2 weeks prior to enrolment. Subjects with prostate cancer should remain on luteinizing hormone releasing hormone (LHRH) agonists or antagonists. Subjects with prostate cancer may also remain on low-dose prednisone or prednisolone (up to 10 mg/day) and still be eligible for this study.
  - d. In addition, any therapy-related toxicity must have resolved to Grade 1 or less, with the exception of alopecia (acceptable at any Grade) and peripheral neuropathy (which must be Grade 2 or less prior to enrollment).
3. Therapeutic anticoagulation (e.g., warfarin, heparin) must be discontinued 7 days prior to the first dose of GSK2820151 and coagulation parameters must be normalized prior to the first dose of GSK2820151. Low (prophylactic) dose low molecular weight heparin (LMWH) is permitted. In addition, INR must be monitored in accordance with local institutional practices.
  4. Current use of a prohibited medication or planned use of any forbidden medications during treatment with GSK2820151 (see Section 7.1.2 for the list of medications).

**NOTE:** Aspirin up to 100mg PO daily is allowed. Concurrent use of non-steroidal anti-inflammatory drugs (NSAIDs) will be excluded except for cases where NSAIDs provide benefit over other analgesics (see Section 7.1.2 for details).

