5. Evidence of severe or uncontrolled systemic diseases (e.g., unstable or uncompensated respiratory, hepatic, renal, cardiac disease, or clinically significant bleeding episodes). Any serious and/or unstable pre-existing medical (aside from malignancy), psychiatric disorder, or other conditions that could interfere with subject's safety, obtaining informed consent or compliance to the study procedures, in the opinion of the Investigator.
6. Symptomatic or untreated leptomeningeal or brain metastases or spinal cord compression.

**NOTE:** Subjects previously treated for these conditions that have had stable central nervous system (CNS) disease (verified with consecutive imaging studies) for >1months, are asymptomatic and off corticosteroids, or are on stable dose of corticosteroids for at least 1 month prior to study Day 1 are permitted. Stability of brain metastases must be confirmed with imaging. Subject treated with gamma knife therapy can be enrolled 2 weeks post-procedure as long as there are no post-

procedure complications/stable. In addition, subjects treated or currently taking enzyme-inducing anticonvulsant (EIA) are allowed on study.

7. Cardiac abnormalities as evidenced by any of the following:
  - History of or current “untreated” clinically significant uncontrolled arrhythmias.
  - Clinically significant conduction abnormalities or arrhythmias
  - Presence of cardiac pacemaker
  - History or evidence of current  $\geq$ Class II congestive heart failure as defined by New York Heart Association (NYHA).
  - History of acute coronary syndromes (including unstable angina and myocardial infarction), coronary angioplasty, or stenting within the past 3 months. Subjects with a history of stent placement requiring ongoing antithrombotic therapy (e.g., clopidogrel, prasugrel) will not be permitted to enroll.
8. Following electrocardiogram (ECG) finding:
  - Baseline corrected QT (Fridericia’s formula) interval (QTcF)  $\geq$ 450 msec

**NOTE:** Any clinically significant ECG assessments should be reviewed by the site cardiologist prior to study entry.
9. Any of the following liver findings:
  - ALT  $>$ 2.5xULN
  - ALT  $>$  5xULN with liver metastases/tumor infiltration
  - Bilirubin  $>$ 1.5xULN (isolated bilirubin  $>$ 1.5xULN is acceptable if bilirubin is fractionated and direct bilirubin  $<$ 35%).

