  - Current active liver or biliary disease (with the exception of Gilbert’s syndrome or asymptomatic gallstones, liver metastases or otherwise stable chronic liver disease per investigator assessment).

**NOTE:** Stable chronic liver disease should generally be defined by the absence of ascites, encephalopathy, coagulopathy, hypoalbuminaemia, esophageal or gastric varices, persistent jaundice or cirrhosis
10. Presence of hepatitis B surface antigen (HBsAg) or positive hepatitis C antibody test result at screening or within 3 months prior to first dose of study treatment. History of known HIV infection.

**NOTE:** Subjects with positive Hepatitis C antibody due to prior resolved disease can be enrolled only if a confirmatory negative Hepatitis C RNA polymerase chain reaction (PCR) is obtained.
11. Any serious known immediate or delayed hypersensitivity reaction(s) to GSK2820151 or idiosyncrasy to drugs chemically related to the investigational drug.

12. Hemoptysis > 1 teaspoon in 24 hours within the last 28 days.
13. Subjects with a history of known bleeding disorder(s) or history of clinical significant hemorrhage ( e.g., gastrointestinal, neurologic) within the last 6 months.
14. Any clinically significant gastrointestinal (GI) abnormalities that may alter absorption such as malabsorption syndrome or major resection of the stomach and/or bowels.

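### In subjects with liver metastases, Table 4 admits INR values that already meet the Appendix 3 INR stopping row wherever the laboratory's INR upper limit is above 1.0

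*Protocol*

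**What the plan says.** **Entry.** Protocol Section 5.1, Table 4, caps INR at 1.5×ULN for every subject. ALT is capped at 2.5×ULN, except that a value below 5 times "ULN is acceptable for subjects with documented liver metastases/tumor infiltration".

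**Stopping.** Appendix 3 has a separate set of six stopping rows for subjects with documented liver metastases or infiltration and entry ALT above 2.5 and up to 5×ULN. Its INR row combines ALT of at least 3×ULN with "INR>1.5, if INR measured". The ALT Increase row in the same set is built differently: ALT must also be at least "1.5x baseline value that persists for" four weeks or more. Any liver stopping event leads to immediate discontinuation, and restart needs sponsor governance approval. Footnote 2 makes one exception to the INR limit: "the threshold value stated will not apply to subjects receiving anticoagulants".

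**Schedule.** INR is part of the coagulation panel (Table 11). Table 8 schedules that panel at screening, W1D1, W1D6, W2D1, W3D1 and later visits, so the condition that INR be measured will be met.

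**The concern.** The entry limit moves with the laboratory's ULN and the stopping limit does not. For a stratum defined by abnormal liver values at entry, one would expect the stopping rules to respond to worsening, or to begin above what entry allows. If the INR row does neither, a subject can be enrolled, dosed for a few days and then stopped on values that were acceptable at screening.

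The subject then bears the first doses of a first-in-human drug and the follow-up work-up for an INR event: repeat chemistries within 24 hours, twice-weekly monitoring, serology, and imaging and/or biopsy. The trial may lose an evaluable subject. In the accelerated phase, with one subject per dose level, that means enrolling another subject at the same dose.

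**Working it through.** No figure in the plan covers this point, so the check compares the two sets of limits.

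**Inputs.** Entry (Table 4): INR ≤1.5×ULN; ALT <5×ULN with liver metastases. Stop (Appendix 3, liver-metastasis stratum): ALT ≥3×ULN and INR >1.5. The INR ULN is not in the documents, because Section 8.3.9 leaves reference ranges to the laboratory. A range of 1.0 to 1.2 is assumed.

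**Step 1, overlap.** In ALT, entry below 5 and stop from 3 overlap at 3 to <5×ULN. In INR, the overlap runs from above 1.5 up to 1.5 × ULN, so it exists only if the ULN exceeds 1.0.

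| INR ULN | Highest eligible INR (1.5 × ULN) | INR values both eligible and stopping |
|---|---|---|
| 1.0 | 1.50 | none |
| 1.1 | 1.65 | above 1.5 to 1.65 |
| 1.2 | 1.80 | above 1.5 to 1.80 |

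Example at ULN 1.1: ALT 3.5×ULN with INR 1.6 satisfies both Table 4 limits and also meets the stop. ALT 2.8×ULN with the same INR is eligible and does not meet it.

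**Step 2, the other five rows.** The ALT-absolute row needs at least 2× baseline. The ALT-increase, cannot-monitor and symptomatic rows each need at least 1.5× baseline. Unchanged values have a ratio of 1.0, so none of these four is met. The bilirubin row has no baseline term, but it needs ≥2×ULN with more than 35% direct. Table 4 admits up to 1.5×ULN, and an isolated higher value "is acceptable if bilirubin is fractionated and direct bilirubin" is below 35% or the subject has Gilbert's syndrome. Leaving aside Gilbert's syndrome and footnote 1 (the rule where fractionation is not immediately available), no eligible value meets that row. INR is the one row of six that overlaps entry.

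**Step 3, timing and doses (Section 6.1).** Scheduled doses in the 4-week window are 4 + 5 + 7 + 7 = 23. The 75% rule in Section 4.2.4 needs 0.75 × 23 = 17.25, so 18 doses. Cumulative doses are 4 by W1D6, 9 by the end of Week 2, 16 by the end of Week 3, 17 on W4D1 and 18 on W4D2. W1D1 blood is taken before dosing, so W1D6 is the first on-treatment INR. A stop there leaves 4/23 = 17% of doses. At W3D1, pre-dose, it is 9/23 = 39%. Every scheduled INR in the window (W1D6, W2D1, W3D1) comes before the 18th dose. A subject stopped at any of them is replaced unless the reason is a DLT.

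**Step 4, does other eligibility text close the gap?** Section 5.2, exclusion 3, says "coagulation parameters must be normalized prior to the first dose of GSK2820151", but this belongs to the criterion on stopping therapeutic anticoagulation. Read as a general rule, it would contradict Table 4. The note on absence of coagulopathy under exclusion 9 defines stable chronic liver disease, and the exception it explains is worded "liver metastases or otherwise stable chronic liver disease per investigator assessment", which lists metastases separately. Neither sets an INR limit for this stratum.

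**The case against.** **The absolute limit looks deliberate.** The bilirubin and INR rows are identical in both strata, while the other four were adapted to baseline. Footnote 2 ties these two rows to possible severe liver injury. This stands, and it is a good reason to leave the stopping row alone. It does not explain why entry should admit values that the row forbids.

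**Exclusion 5 may already cover such a subject.** It bars "Evidence of severe or uncontrolled systemic diseases", including uncompensated hepatic disease, and that sentence carries no opinion-of-the-investigator qualifier. Appendix 4, on rechallenge, counts INR ≥1.5 among its markers of severe liver injury. An investigator who sees the screening values could reasonably use this route. But it gives no number and does not displace Table 4's explicit limit, so the outcome depends on who reads it.

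**A reader might infer that every such stop is also an SAE.** Appendix 3 footnote 2 and item g of Section 14.6.2 point that way. However, Section 14.6.1 excludes from AEs laboratory findings due to the underlying disease that are not more severe than expected, and Section 14.6.2 says that what is not an AE cannot be an SAE. The documents pull in both directions, so SAE status is ambiguous.

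**A reader might infer a biased MTD.** The specific liver DLT criterion in Table 3 does not use INR, and a DLT must be attributed to treatment. The documents do not support that inference.

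**Practical weight is small.** The SAP records early termination with 5 subjects enrolled. This stands: the point matters mainly if these criteria are reused.

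**Conclusion.** The mismatch is real and minor. It needs all of the following: an INR ULN above 1.0, documented liver metastases with entry ALT 3 to <5×ULN, entry INR above 1.5, and no anticoagulant. The documents give no frequency for this combination, and few subjects are likely to have it. For those who do, immediate discontinuation applies at W1D6 without any change, followed by replacement if the event is not a DLT.

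It would go too far to say that the conflict arises at every site: at a ULN of 1.0 or below there is none. Figure 4, the algorithm for this stratum, is not shown and could not be checked. Confidence is medium.

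**What to change.** Add one line to Table 4: for subjects with documented liver metastases and entry ALT ≥3×ULN who are not receiving anticoagulants, require INR ≤1.5 (absolute) in addition to ≤1.5×ULN. The anticoagulant wording matches footnote 2; without it, the line would exclude subjects on permitted prophylactic doses to whom the stopping limit does not apply. Leave the Appendix 3 INR row, footnote 2 and SAE item g unchanged, so that no safety rule is loosened.

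**Cost.** No new assessment is needed, because INR and ALT are already drawn at screening. A few subjects are excluded before dosing. The line does not remove every near-miss. With a ULN of 1.1, a subject entering at ALT 2.9×ULN and INR 1.6 stays eligible and meets the stop after a rise of 0.1×ULN (0.1/2.9 = about 3%). That remaining case involves an actual, if small, rise in ALT and seems acceptable.

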#### 4.2.1. Planned Dose Levels

Projected dose levels are 3 mg, 6 mg, 12 mg, 20 mg, 40 mg, 60 mg, 100 mg, 150 mg, 200 mg, and 300 mg. Additional doses and schedules may be explored based on emerging safety, PK, and PD data.

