## 4.5. Dose Justification

### 4.5.1. Human Pharmacokinetic Extrapolation

Human pharmacokinetics was predicted based on three species (mouse, rat and dog) using different allometric extrapolation. Whole blood human clearance predicted from mean of allometry was 6.5 ml/min/kg (~30% hepatic blood flow). Volume of distribution at steady state was predicted to be 2.8 L/kg with a moderate half life of ~5hr. Bioavailability is predicted to be ~69%.

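### Appendix 3 fixes the liver-event PK sample at 2 days after the last dose, about 9.6 predicted half-lives, and bars it at other times, so it is unlikely to inform exposure at the event

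*Protocol*

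**What the plan says.** Protocol Appendix 3 (Section 14.3) lists what must be done after any liver stopping event. Study treatment stops at once. Among the follow-up assessments is a "Blood sample for pharmacokinetic (PK) analysis, obtained 2 days after last dose". The entry names one time point and gives no window around it.

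Footnote 6 to that entry requires the dates and times of the draw and of the last dose to be recorded. It then gives two situations in which the sample is omitted. One is that the time of the last dose cannot be estimated. The other reads "OR a PK sample cannot be collected in the time period indicated above, do not obtain a PK sample".

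The monitoring instructions in the same table begin, for both groups of events, "Repeat liver chemistries (include ALT, aspartate aminotransferase [AST], alkaline phosphatase, bilirubin) and perform liver event follow up assessments within". The limit that follows is 24 h for bilirubin or INR events and 24-72 h for all other criteria.

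The expected kinetics are in Section 4.5.1: "Volume of distribution at steady state was predicted to be 2.8 L/kg with a moderate half life of ~5hr". That section also gives "Whole blood human clearance predicted from mean of allometry was 6.5 ml/min/kg (~30% hepatic blood flow") and a bioavailability of about 69%.

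Three other places bear on the point. The synopsis (Measurements) permits one-off PK draws for severe or worrying events. Section 8.4.1 permits PK times to be moved or added without an amendment. Section 6.6 uses a window for the overdose sample: up to 3 days after the last dose, if the medical monitor asks for it.

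**The concern.** Appendix 3 says its criteria serve in part to establish what caused a liver event, and a drug concentration helps most with that when it reflects exposure around the event. By 48 h nearly all of a drug with a 5 h half-life has gone. A very low result would then look much the same in a subject with ordinary exposure and one with high exposure.

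Footnote 6 makes this worse. Read as written, it tells a site that sees the subject a few hours after the last dose not to take the Appendix 3 sample then, and one that misses the 2-day point not to take it at all.

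The timing matters most for events away from the scheduled PK days. Tables 7, 9 and 10 schedule PK at Week 1 Days 1 and 5, Week 2 Day 4, Week 3 Day 4 and Week 9 Day 1. For an event between the last two of these, or after Week 9, the Appendix 3 sample is the only concentration that the schedule requires near the event.

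**Working it through.** **Inputs.** Clearance 6.5 mL/min/kg, volume 2.8 L/kg, bioavailability 69% and half-life about 5 h (Section 4.5.1); body weight 70 kg and predicted AUC of 78.8 at 3 mg (Section 4.5.2); dose levels 3 to 300 mg (Section 4.2.1); sample at 48 h (Appendix 3). One compartment and instantaneous absorption are assumed.

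**Reproducing the plan's figures.**
- Half-life = ln 2 × V / CL = 0.693 × 2800 / 6.5 = 299 min = 4.98 h, against about 5 h stated.
- AUC at 3 mg = F × dose / CL = 0.69 × 3,000,000 ng / (6.5 × 60 × 70 mL/h) = 75.8 ng·h/mL, 3.8% below the stated 78.8.

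**Half-lives elapsed and fraction left.**
- 48 h: 48 / 5 = 9.6 half-lives; 2^(−9.6) = 0.0013, or 0.13%.
- 24 h: 24 / 5 = 4.8 half-lives; 2^(−4.8) = 0.036, or 3.6%.

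These fractions depend on the half-life alone, so weight and bioavailability do not enter.

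**Sensitivity to the half-life.**

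| Half-life | Left at 24 h | Left at 48 h |
|---|---|---|
| 4 h | 1.6% | 0.02% |
| 5 h | 3.6% | 0.13% |
| 6 h | 6.3% | 0.39% |
| 10 h | 19% | 3.6% |
| 24 h | 50% | 25% |

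Between half-lives of 4 h and 6 h the 48 h level changes 2^(−8) / 2^(−12) = 16-fold; the 24 h level changes 2^(−4) / 2^(−6) = 4-fold. A single late value is therefore hard to trace back to exposure at the event, even when it can be measured.

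**Approximate concentrations at 48 h.** The initial level at 3 mg is 0.69 × 3 mg / (2.8 × 70 L) = 10.6 ng/mL, falling to 0.014 ng/mL at 48 h. The 48 h level is 0.45 ng/mL at 100 mg and 1.4 ng/mL at 300 mg. No quantification limit is stated. For an assumed limit of 0.1 to 1 ng/mL, the sample would be unquantifiable below about 22 to 220 mg, which is 4 to 9 of the 10 dose levels. These concentrations apply a whole-blood clearance to plasma samples with no blood-to-plasma ratio, so they are indicative only.

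**Fit with the follow-up limits.** Take the limits as running from the event, and let the last dose be t hours before it. The sample is then due 48 − t hours after the event.
- The 24 h limit is met only if t is at least 24.
- If t is below 24, the sample falls more than 24 and up to 48 h after the event. That is too late for bilirubin or INR events, but inside the 24-72 h limit for the others.

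**The case against.** Several points on the other side stand.

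- **The half-life is a prediction.** It is an allometric extrapolation from mouse, rat and dog, and the documents report no observed human value. At 10 h, 3.6% would remain at 48 h, about 28 times the base case. Section 6.6 expects monitoring after overdose to last at least 28 days, until drug is undetectable, and Table 9 schedules a 33 h sample after a single dose. The plan does not treat late samples as worthless. Impaired elimination in liver injury could also leave measurable drug, though that would show persistence rather than exposure at the event.
- **Earlier draws are not forbidden altogether.** A reader might infer that a subject seen 4 to 24 h after dosing may not be sampled. Footnote 6 limits only the Appendix 3 sample; the synopsis and Section 8.4.1 allow others. They are optional, however, do not mention liver events and do not override the footnote.
- **Other exposure data exist.** Tables 9 and 10 schedule serial sampling for every subject, including those in one-subject cohorts. Section 8.4 plans population PK, and Section 8.5 allows predicted exposures. With predicted accumulation of only 1 / (1 − 2^(−4.8)) = 1.04-fold, exposure could be estimated from the subject's own profile and dosing record. That is an estimate, and it assumes that clearance has not changed with the liver event.
- **The timing conflict is partial.** It needs a bilirubin or INR event and a recent dose.
- **The practical reach is small.** The SAP introduction records early termination with 5 subjects enrolled. The sample feeds no primary endpoint, DLT rule or escalation rule.

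**Conclusion.** The point holds as a weakness in one safety sample. On the protocol's own predicted half-life, the required time leaves about 0.13% of the drug, against 3.6% at 24 h, and footnote 6 rules out the Appendix 3 sample at any more useful time. The sample is therefore unlikely to inform exposure at the event. For bilirubin or INR events with a dose less than 24 h earlier, the required time also cannot be reconciled with the 24 h follow-up limit.

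A reader might go further and infer that the sample cannot show exposure, or that it would be unquantifiable at most doses. The documents support neither. The first needs an observed half-life and a quantification limit, and neither is given. The second depends wholly on the assumed limit: at 0.1 ng/mL only 4 of 10 dose levels are affected. The relative comparison is firmer: at every half-life in the table more drug remains at 24 h than at 48 h, so an earlier sample is the more informative one.

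**What to change.** In Appendix 3, replace the fixed 2-day time with a sample drawn at the first contact for the event, together with the repeat liver chemistries and as soon as possible after the last dose. Dose and draw times should be recorded, as footnote 6 already requires. If first contact comes later than 48 h, the recorded times still allow the value to be interpreted.

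In footnote 6, remove the ban only for samples outside the stated period. Keep it where the last-dose time cannot be estimated, because such a concentration could not be placed in time.

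Then reconcile the entry and footnote with the 24 h and 24-72 h follow-up limits, the optional draws in the synopsis and Section 8.4.1, and the overdose window in Section 6.6.

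The cost is amendment wording and a matching change to the Laboratory Manual; the same single tube is taken at a contact already required. With this study ended, the practical value is in not carrying the wording into another protocol.
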